8.7.4. Primary analyses

The primary analyses will be conducted in the following study population/analysis set: pregnancies ending in singleton/multiple live birth, stillbirth. The assessment of the outcomes stillbirth and major congenital malformations will include stillbirths; the other primary outcomes assessment will exclude stillbirths.

8.7.4.1. Descriptive analysis

- Pregabalin use in pregnancy will be described as the number and proportion of pregnancies exposed in the first trimester, and in any trimester. Number and proportion of pregnancies with pregabalin monotherapy will be reported. Cumulative dose during first trimester and any trimester will be described based on the amount of dispensings during a relevant period. Use of lamotrigine and duloxetine will be similarly described.

- Distributions of the characteristics of the study population will be tabulated according to pregabalin exposure categories: first trimester (exposed/unexposed); any trimester (exposed/unexposed) and separately for the monotherapy subgroup. Categorical variables will be summarized using frequencies and proportions; continuous variables using either mean and standard deviation (SD), or median and interquartile range (IQR) as appropriate.
- Distribution of maternal and offspring characteristics in the study population will be tabulated according to pregabalin and the active comparator categories, as above. All descriptive tables will be constructed including stillbirths.
- Crude prevalence of the major congenital malformations will be reported according to first-trimester exposure to pregabalin (overall and in the subcategory of monotherapy) and each comparator (overall for all comparators including not exposed and in the subcategory of monotherapy for lamotrigine and duloxetine). In addition overall prevalence of malformations in the whole general population will be presented. Crude prevalence of the other birth outcomes (stillbirth, low birth weight, small for gestational age (SGA), preterm birth, low Apgar score at 5 minutes and microcephaly) will be reported according to any trimester exposure to pregabalin and each comparator, in the same fashion.

Major congenital malformation outcomes

Major congenital malformations (any, each major malformation type sample size permitting), among pregnancies ending in a live or a stillbirth pregnancies exposed to pregabalin during the first trimester will be compared against each of the comparators estimating crude and adjusted prevalence ratios in log-binomial regression.

Birth outcomes other than major congenital malformations

For birth outcomes other than major congenital malformations, any-trimester pregabalin exposed pregnancies will be compared against each of the comparators estimating crude and adjusted prevalence ratios in log-binomial regression. With the exception of stillbirth, all remaining birth outcomes will be assessed in pregnancies ending in a live birth

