7. RESEARCH QUESTION AND OBJECTIVES

The study objectives are to describe the use of pregabalin exposure in pregnancy and to estimate the risk of major congenital malformations, birth outcomes other than congenital malformations and neurodevelopmental outcomes with the use of pregabalin. Association between pregabalin exposure and a given safety outcome will be assessed for pregabalin exposure during a relevant gestational period using, alternatively, unexposed subjects and subjects exposed to treatments with indications similar to those of pregabalin (active comparators); effect exposure to pregabalin monotherapy will be assessed in a sensitivity analysis.

The specific primary objectives of the study are to:

- Describe use of pregabalin, lamotrigine, and duloxetine during pregnancy overall, by trimester and by calendar year of delivery in pregnancies ending in live or stillbirths, as characterized by
 - Prevalence of use (proportion of pregnancies with 1 or more dispensing of a given drug),
 - Distribution of therapeutic indications among the exposed pregnancies (epilepsy, GAD, neuropathic pain),
 - Cumulative dose, based on dispensings count and amount dispensed in each;
- Describe the prevalence of (proportion of live or stillborn children with) major congenital malformations after first-trimester in-utero exposure to pregabalin (yes/no); after first-trimester exposure to lamotrigine, after first-trimester exposure to duloxetine, after first-trimester exposure to lamotrigine or duloxetine, in pregnancies ending in live or still birth; in live or stillborn children unexposed to antiepileptics in the first trimester; and in the total population of live or stillborn children;
- Estimate the association between first-trimester exposure to pregabalin and prevalence of major congenital malformations, as compared with no first-trimester exposure to pregabalin, with first-trimester exposure to lamotrigine, with first-trimester exposure to duloxetine, and first-trimester exposure to lamotrigine or duloxetine, in live or stillborn children;
- Describe the prevalence of birth outcomes other than major congenital malformations (listed in [Section 8.3.2.1](#)) according to exposure (yes/no) to pregabalin any time

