8.3. Variables

8.3.1. Exposures

For the purposes of timing of exposure, trimesters of pregnancy will be defined as follows:

- First trimester: from the first day of the last menstrual period (LMP)-90 days to LMP+97 days (both dates inclusive);
- Second trimester: from LMP+98 days to LMP+202 days (both dates inclusive);
- Third trimester: from LMP+203 days (inclusive) until pregnancy end date (not included).

Exposure during the first trimester

Pregabalin exposure during the first trimester will be defined as at least one maternal dispensing of pregabalin during the first trimester. Pregabalin monotherapy in the first trimester will be defined as first-trimester exposure to pregabalin and no first-trimester dispensing for any other AED.

Comparators:

Unexposed to pregabalin during the first trimester comparator is defined as pregnancies without a dispensing for pregabalin or any other AED, including lamotrigine or duloxetine, during the first trimester.

Lamotrigine exposure in the first trimester is defined by at least one dispensing of lamotrigine during the first trimester. Lamotrigine monotherapy in the first trimester will be defined as first-trimester exposure to lamotrigine and no first-trimester dispensing for any other AED.

Duloxetine exposure in the first trimester is defined by at least one dispensing of duloxetine during the first trimester. Duloxetine monotherapy in the first trimester will be defined as first-trimester exposure to duloxetine and no first-trimester dispensing for any AED.

Lamotrigine or duloxetine exposure in the first trimester is defined by at least one dispensing of lamotrigine or duloxetine or both during the first trimester. Lamotrigine or duloxetine monotherapy in the first trimester will be defined as first-trimester dispensing of lamotrigine or duloxetine or both and no first-trimester dispensing for any other AED.

For analyses that use lamotrigine as the comparator, pregnancies exposed to both pregabalin and lamotrigine in the first trimester will be excluded. For analyses that use duloxetine as the comparator, pregnancies exposed to both pregabalin and duloxetine in the first trimester will be excluded.

Exposure any time during pregnancy

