Pregabalin exposure any time during pregnancy is defined by at least one dispensing of pregabalin during any trimester. Pregabalin monotherapy any time during pregnancy will be defined as any-pregnancy exposure to pregabalin and no dispensing for any other AED during any trimester.

Comparators:

Unexposed to pregabalin during any trimester comparator is defined as pregnancies without dispensing for pregabalin or other AEDs including lamotrigine, or duloxetine during any trimester.

Lamotrigine exposure any time during pregnancy is defined by at least one dispensing of lamotrigine during any trimester. Lamotrigine monotherapy any time during pregnancy will be defined as any-pregnancy exposure to lamotrigine and no dispensing for any other AED during any trimester.

Duloxetine exposure any time during pregnancy is defined by at least one dispensing of duloxetine during any trimester. Duloxetine monotherapy any time during pregnancy will be defined as any-pregnancy exposure to duloxetine and no dispensing for any AED during any trimester.

Lamotrigine or duloxetine exposure any time during pregnancy defined by at least one dispensing of lamotrigine or duloxetine or both during any trimester. Lamotrigine or duloxetine monotherapy any time during pregnancy will be defined as any-pregnancy exposure to lamotrigine or duloxetine or both and no dispensing for any other AED during any trimester.

For analyses that use lamotrigine as the comparator pregnancies exposed to both pregabalin and lamotrigine in any trimester will be excluded. For analyses that use duloxetine as the comparator pregnancies exposed to both pregabalin and duloxetine in any trimester will be excluded.

In a sensitivity analysis, monotherapy with pregabalin, lamotrigine, and/or duloxetine will be defined by absence of other AED, selective serotonin reuptake inhibitors, or benzodiazepines.

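### First-trimester cumulative dose is summed over a 188-day window that starts 90 days before LMP, so the drug-use tables count preconception supply as dose in pregnancy

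*Protocol*

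**What the plan says.** Section 7 makes description of drug use the first primary objective: "Describe use of pregabalin, lamotrigine, and duloxetine during pregnancy overall, by trimester and by calendar year of delivery in pregnancies ending in live or stillbirths". Two of the measures listed under it are "Prevalence of use (proportion of pregnancies with 1 or more dispensing of a given drug" and "Cumulative dose, based on dispensings count and amount dispensed in each". The Abstract also lists use by trimester among the primary objectives, and its data-analysis paragraph repeats prevalence by trimester.

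Section 8.3.1 fixes the windows. The earliest one is worded as "First trimester: from the first day of the last menstrual period (LMP)-90 days to LMP+97 days (both dates inclusive". The next covers days 98 to 202 after LMP, and the last begins on day 203 and stops short of the day on which the pregnancy ends.

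Any-time exposure is built from the same windows: "Pregabalin exposure any time during pregnancy is defined by at least one dispensing of pregabalin during any trimester". It therefore also reaches back to LMP-90.

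Section 8.7.4.1 then sets the dose rule: "Cumulative dose during first trimester and any trimester will be described based on the amount of dispensings during a relevant period". It names only the first trimester and any trimester. Neither section gives another dose window or any adjustment for supply dispensed before LMP or for differences in window length.

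**The concern.** A 90-day look-back is a reasonable device for classifying a pregnancy as exposed or not, because a pack collected before LMP may still be in use after it. Using the same window to add up dose is a different matter: the full amount of every pack dispensed in those 90 days is credited to the first trimester. The protocol keeps the two periods apart elsewhere. Section 8.2 speaks of gestation and preconception separately, and Section 8.9 places study entry at the estimated conception date.

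The three windows also differ in length. Any measure that accumulates over a window, whether an amount dispensed or the chance of at least one dispensing, is not comparable between trimesters unless length is allowed for.

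At stake is the reading of a primary descriptive objective. A reader of the tables could take the first-trimester total as dose in early pregnancy, or take a lower third-trimester figure as evidence of reduced use.

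**Working it through.** The protocol prints no window length in days and no dose total, so there is no figure of its own to reproduce. The boundaries come from Section 8.3.1. Pregnancy length and dispensing pattern are not given and are treated as assumptions.

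**Window lengths (inclusive day counts)**
- First trimester: 90 + 97 + 1 = 188 days, of which 90 precede LMP and 98 run from LMP onward.
- Second: 202 - 98 + 1 = 105 days.
- Third: end day - 203. This is 77 days for a 280-day pregnancy, 56 days for 259 and 91 days for 294.

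**First-trimester dose, continuous user**
- Share dispensed before LMP: 90/188 = 47.9%.
- Reported amount over amount dispensed from LMP to LMP+97: 188/98 = 1.92.
- Simulated continuous users with random refill phase gave about 1.92 for every pack length tried from 28 to 100 days, so the average factor does not depend on pack size.

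**First-trimester dose, other patterns**
- Stops at LMP+56: (90 + 56)/56 = 2.61.
- Stops at LMP+35: (90 + 35)/35 = 3.57.
- Stops at LMP: the whole reported dose is pre-LMP supply.
- Starts after LMP: no overstatement from this source.

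**Any-trimester dose, continuous user**
- 280 days: (188 + 105 + 77)/280 = 370/280 = 1.32.
- 259 days: 349/259 = 1.35. 294 days: 384/294 = 1.31.

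**Amount dispensed by trimester, constant use, 280 days**
- The amounts stand as 188 : 105 : 77. First to second: 1 - 105/188 = 44% lower. Second to third: 1 - 77/105 = 27% lower. Neither fall reflects a change in use.

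**Prevalence of at least one dispensing, constant use, 280 days**

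| Assumed pattern | First | Second | Third |
|---|---|---|---|
| Regular refills every 77 days or less | 100% | 100% | 100% |
| Regular refills every 90 days | 100% | 100% | 86% |
| Random dispensings, 2 per year | 64% | 44% | 34% |

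The last row uses P = 1 - exp(-2L/365.25) with L = 188, 105 and 77.

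**After separating the preconception days**
- The windows become 98, 105 and 77 days. A steady user's first-trimester amount drops from 188 to 98 days' supply. The random-dispensing first-trimester prevalence becomes 42%. The third window is still the shortest, so the split alone does not make trimesters comparable; a rate per 30 days does so for the amount dispensed.

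**The case against.** The measure is labelled as an amount dispensed, not an amount taken; the window is printed; and Section 8.9 warns that dispensing records may misstate the amount and timing of intake. That is fair, but the caveat is general. It mentions neither the pre-LMP days nor the unequal windows, so it would not tell a reader how to interpret the totals.

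Section 8.7.4.1 plans dose and prevalence only for the first and any trimester, and sets out no trend across trimesters. This stands: the by-trimester problem arises from Section 7 and the Abstract, not from the dose sentence, and nowhere does the protocol say that a fall will be read as discontinuation.

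Cutting the dose window at LMP has a cost of its own. With 90-day packs, a woman who stops at LMP+35 has about a 35/90 = 39% chance of a refill between LMP and stopping. About 61% of such women would then show no first-trimester dose while counting as first-trimester exposed in the malformation analysis. This also stands, and is the reason to keep the full-window total beside the LMP-onward total.

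Table layout may be left to the Annex 3 shells, whose contents are not shown and which might already separate the periods. That could soften the point, but the rule as written in the body of the protocol does not separate them.

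Three stronger readings are tempting and are not supported. One is that first-trimester dose is overstated two-fold for everyone: the protocol gives no refill interval or persistence, and 1.92 belongs to continuous users. Another is that most of the reported first-trimester dose was taken before pregnancy: for a continuous user the pre-LMP share dispensed is 48%, under half, and some of it may be taken after LMP. The third is that prevalence must fall across trimesters: with regular refills of 77 days or less it does not.

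**Conclusion.** The point holds for the drug-use description. Followed as written, the plan counts 90 days of preconception supply as dose in the first trimester and in pregnancy, under a primary objective. The size is about 1.9-fold for the first trimester and about 1.3-fold for any trimester in continuous users (1.31 to 1.35 for pregnancies of 259 to 294 days). It ranges from nothing for women who start after LMP to 3.57 for a stop at LMP+35, and is higher for earlier stops. Early stopping is plausible, since Section 6 cites a label advising against use in pregnancy unless clearly necessary, but its frequency is unknown.

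In by-trimester reporting, the artificial fall in amount dispensed is certain for steady users; a fall in prevalence is possible only for irregular or long-interval refillers.

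A reader might infer that the malformation and other outcome comparisons are distorted as well. They are not affected by this point: every planned contrast uses yes/no exposure and none uses cumulative dose.

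**What to change.** In Section 8.7.4.1 and the matching table shells only:

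1. Report dispensings in LMP-90 to LMP-1 in a separate preconception column.
2. Give first-trimester and any-trimester cumulative dose counted from LMP onward, beside the full-window total. The second figure keeps the tables aligned with the exposure definition and avoids showing early stoppers only as zero.
3. Add the amount dispensed per 30 days of window for each period reported.
4. Footnote that part of a pack dispensed shortly before LMP may be taken after it.

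Leave the yes/no exposure definitions in Section 8.3.1 as they are. Dispensing dates are already held in each country's data, so the cost is an extra column, a second dose total, a rate and a footnote in the descriptive tables. No new data or models are needed.

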This non-interventional study will evaluate the pattern of use and safety of pregabalin in pregnancy using data on all pregnancies identifiable from population-based registries in Denmark, Finland, Norway, and Sweden. The primary analyses will consist of a comparison of exposed vs unexposed to pregabalin during the relevant period of pregnancy. To control for confounding by indication,¹³ in addition to assessing the risk of study outcomes according to exposure to pregabalin during pregnancy, the study outcomes will also be assessed in pregnancies exposed to agents with similar pregabalin indications – lamotrigine (epilepsy) and duloxetine (neuropathic pain, GAD).

This non-interventional study is designated as a Post-Authorisation Safety Study (PASS) and is a commitment to the EMA).

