8.2. Setting

[figure not shown]
This study will be conducted using data from four Nordic countries: Denmark, Finland, Norway, and Sweden (listed alphabetically) in each country, all live births and stillbirths are recorded in the birth registries (in all countries from gestational week 22 from July 2008 onwards; in Sweden, from gestational week 28 until July 2008). During those periods there were approximately 580,000 – 730,000 live births in each of Denmark, Finland, and Norway, and 800,000 in Sweden.¹⁶ The start of the study period in each country is selected to ensure availability of pregabalin and the candidate comparator on the market and availability of data on outpatient dispensings for at least 12 months before the end of the earliest identified pregnancy. For example, pregnancy ending at term with a live birth on 1 January 2005 in Denmark will have prescription history from 1 January 2004, thus covering the 9 months of gestation and 3 months preconception.

Population-based healthcare registries in Nordic countries are an optimal setting for examining safety of medicines in pregnancy. Their most important strengths are capture of all births and, in some cases, clinically relevant birth and postnatal outcomes; routine capture of dispensings of prescription medications to pregnant women; extensive information about maternal and offspring health outcomes; and exact linkage between the maternal and the offspring record. Thus, unlike studies based e.g., on data from TIS, there is no risk of bias by self-referral, recall, or access to health care. Dispensings of medicines represent a better proxy of actual drug intake than do issued prescriptions (primary compliance), reducing misclassification of the actual drug intake.

Study population

The study population consists of all pregnancies identified in the respective administrative registries from 1 January 2005 to 31 December 2015 in Denmark, Finland, and Norway and all pregnancies identified from 1 July 2006 to 31 December 2013 in Sweden, Figure 1 .

Figure 1. Study population flow diagram

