8.3.2.1. Primary Outcomes (Birth outcomes)

- Major congenital malformations, any and specific, according to the European Network of Congenital Anomaly Registers (EUROCAT) classification²⁰
- Stillbirth, as recorded in each country's birth registry
- Low birth weight (birth weight < 2500 g)
- Small for gestational age (SGA), defined, for singleton pregnancies, as a dichotomous variable (yes/no) of birth weight below 2 standard deviations (SDs) of sex- and gestational week specific distributions, using country-specific reference standard.^{19,21} SGA non-singleton gestations will be defined if appropriate reference standard can be defined/identified; otherwise set to missing.
- Preterm birth, defined as gestational age <37 weeks
- Low Apgar score at 5 minutes, defined as a dichotomous variable (score 0-6 vs. score 7-10)
- Microcephaly, defined as a dichotomous variable (yes/no) of head circumference at birth (cm) smaller than 2 SD of sex- and gestational week specific distribution, using country-specific reference standard

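### For preterm birth and stillbirth, any-trimester exposure is counted up to delivery, so with no true effect the prevalence ratio versus the unexposed group is biased below 1, by an amount the protocol does not allow to be fixed

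*Protocol*

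**What the plan says.** Section 8.3.1 of the protocol states: "Pregabalin exposure any time during pregnancy is defined by at least one dispensing of pregabalin during any trimester". The last window has no fixed length: "Third trimester: from LMP+203 days (inclusive) until pregnancy end date (not included". The unexposed group for the same period is "pregnancies without dispensing for pregabalin or other AEDs including lamotrigine, or duloxetine during any trimester". Section 8.7.4.1, under birth outcomes other than malformations, then specifies that "any-trimester pregabalin exposed pregnancies will be compared against each of the comparators estimating crude and adjusted prevalence ratios in log-binomial regression". Exposure therefore enters as a fixed ever/never status.

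The outcomes analysed this way include stillbirth, low birth weight and, from Section 8.3.2.1, "Preterm birth, defined as gestational age <37 weeks". Section 6 names the leading contrast: "The primary analyses will consist of a comparison of exposed vs unexposed to pregabalin during the relevant period of pregnancy".

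Nothing elsewhere offsets this:
- The sensitivity analyses in Section 8.7.6 concern terminated pregnancies and the monotherapy definition.
- Section 8.9 does not raise the issue. On study entry it says only that each woman enters at the estimated conception date.
- Item 7.2.2 of the ENCePP checklist (Annex 2), which lists time-related bias among its examples, is ticked as covered by Section 8.9.
- In Section 8.3.3 the medication covariates for these outcomes are also defined over any trimester.

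The Abstract is inconsistent on one point. Its bullet on adjusted ratios for the birth outcomes refers to exposure in the first trimester, whereas its exposure definitions, Section 8.3.1 and Section 8.7.4.1 use any trimester for outcomes other than malformations.

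**The concern.** The length of the exposure window is set by the outcome. A pregnancy that ends at week 30 cannot receive a pack in weeks 30 to 40; a term pregnancy can. A first dispensing at or after 37 weeks can occur only in a birth that is not preterm, so it always adds an exposed non-case. This is immortal-time bias in the exposure definition. Propensity-score weighting on covariates does not remove it.

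Against the unexposed group, window length alone can move a null ratio only downwards. In a post-authorisation safety study that is the direction of false reassurance. The bias also differs between comparators. That matters because Section 8.1 plans to infer the amount of confounding from differences between the estimates obtained with different comparators.

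**Working it through.** **The plan's own figure.** Section 8.5 gives an upper limit of 1.65845 for 3% prevalence, 1,000 exposed, 119:1 allocation and a true ratio of 1.0. The formula exp[(1.96 + 0.8416) × √((1−p)/(n·p) × (1 + 1/119))] returns 1.65844, so it is used below for precision.

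**Late-only shares from Table 4** (Denmark + Finland + Norway + Sweden):

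| Drug | First trimester | Any time | Late-only share |
|---|---|---|---|
| Pregabalin | 200+700+200+400 = 1,500 | 350+900+350+800 = 2,400 | 900/2,400 = 37.5% |
| Lamotrigine | 6,200 | 8,300 | 2,100/8,300 = 25.3% |
| Duloxetine | 1,800 | 3,200 | 1,400/3,200 = 43.8% |

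For pregabalin the share is 22% in Finland, 43% in Denmark and 50% in Sweden. Norway is imputed from Denmark.

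**Null ratio versus unexposed.** Let L be the late-only share. For an outcome delivered on day g after LMP, with late first dispensings uniform from day 98 to day 280:

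PR = (1 − L) + L × (g − 98)/(280 − 98)

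Day 98 is the first day after the first-trimester window ("Second trimester: from LMP+98 days to LMP+202 days (both dates inclusive"). Term at day 280, the uniform spread, and day 245 (35 weeks) as a typical preterm delivery are assumptions.

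- Preterm, g = 245: 0.625 + 0.375 × 147/182 = 0.928. With Finland's share it is 0.957, with Sweden's 0.904.
- A simulation with an assumed gestational-age distribution gives 0.927 to 0.931 for preterm prevalence of 5% to 10%.
- Stillbirth: 0.74 at week 22 (g = 154), 0.83 at week 28 (g = 196), 0.89 at week 32 (g = 224).
- First dispensings that rule out preterm birth: 900 × (280 − 259)/182 ≈ 104 pregnancies, 4.3% of the exposed.

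**Dependence on timing (preterm).**
- All late starts in the second trimester: the window has closed by day 203, so at g = 245 the ratio is 1.00.
- Late starts concentrated soon after LMP+98 (exponential, mean 60 days): about 0.98.
- All late starts uniform in the third trimester: 0.625 + 0.375 × (245 − 203)/(280 − 203) = 0.83. Other assumed gestational-age distributions give 0.81 to 0.83, so about 0.82.

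**Active comparators (preterm, uniform starts).** The comparator ratio at g = 245 is 0.951 for lamotrigine and 0.916 for duloxetine.
- Versus lamotrigine: 0.928/0.951 ≈ 0.975.
- Versus duloxetine: 0.928/0.916 ≈ 1.013.
- Versus either drug: about 0.986.

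**Size against precision (versus unexposed).**
- Preterm, at Table 5's 10% with 2,400 exposed: SE of log PR = √(0.9/240 × 1.0084) = 0.0615. Since log(0.928)/0.0615 = −1.22, 95% interval coverage is about 77% and a falsely protective interval occurs about 23% of the time, instead of 2.5%. At a ratio of 0.925 coverage is 75%; at 0.98 it is 94%.
- Stillbirth, at Table 5's 0.6%: about 14 exposed events, SE about 0.26. A ratio of 0.89 is about 0.44 SE, with coverage about 93%.

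Low birth weight was not computed.

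**The case against.** A reader might infer that these outcomes will look falsely rare after pregabalin against every comparator, and by a known 7%. The documents do not support that.

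- **Timing.** The protocol gives no data on when late first dispensings occur. The 0.93 rests on a uniform spread, and early clustering leaves almost no preterm bias.
- **Late-only share.** Table 4 holds rounded feasibility counts with Norway imputed, and it does not say whether its first trimester starts at LMP−90 as in Section 8.3.1. The Danish figures also disagree. Section 6 says 21% of first-trimester exposed pregnancies had a known indication and Table 1 counts 74 such pregnancies, which implies 74/0.21 ≈ 352, against 200 in Table 4. Table 1 alone gives a similar late-only share (1 − 74/117 = 37%), but only among pregnancies with a recorded indication.
- **Comparators.** Against lamotrigine most of the bias cancels, and against duloxetine the direction slightly reverses.
- **Outcomes.** For stillbirth the bias is generally small relative to its standard error. Sweden's and Finland's preterm ratios (0.90 and 0.96) would be practically indistinguishable, so visible heterogeneity between countries is not established either.
- **Estimand.** A closed window does not answer the stated question about any in utero exposure.

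All of this stands, and it limits size and generality. It does not remove the mechanism: against the unexposed group the direction under the null follows from the definitions, and no planned analysis would reveal it.

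**Conclusion.** The concern holds for preterm birth and stillbirth in the exposed-versus-unexposed contrast, and for low birth weight through its preterm component (not quantified). With no true effect the ratio is biased below 1. For preterm birth the size is about 0.93 under Table 4's approximate 37.5% late-only share and uniform late starts, within a range of about 1.00 to 0.82 set by undocumented timing. At 0.93 the bias exceeds one standard error for a 10% outcome with 2,400 exposed.

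Against lamotrigine (about 0.97) and duloxetine (about 1.01) the bias is small. However, the difference between these values and 0.93 would appear as a between-comparator difference, which Section 8.1 would read as evidence about confounding.

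**What to change.** For preterm birth, stillbirth and low birth weight, and against each comparator, base the analysis on one of:

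1. Exposure in a window that closes before the outcome can occur. This can be dispensing up to LMP+153, the last day before 22 completed weeks (stillbirths are registered "in all countries from gestational week 22 from July 2008 onwards"), or the first-trimester window already defined.
2. A time-updated exposure model on gestational age from week 22, with follow-up closed at 36+6 weeks for preterm birth.

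With a closed window, define the medication covariates of Section 8.3.3 over the same window; otherwise they keep the delivery-dependent period. Re-estimate the corresponding propensity scores of Section 8.7.3.1. Keep the any-trimester result as supplementary, describe the bias in Section 8.9, and reconcile the Abstract's first-trimester wording for birth outcomes with Section 8.7.4.1.

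**Cost.** The dispensing dates are already held. The first-trimester window keeps about 1,500 exposed. Under uniform starts the LMP+153 window keeps 1,500 + 900 × 56/182 ≈ 1,777, about 1,800. Both exceed the planning figure of 1,000. For a 10% outcome the limit ruled out moves from about 1.19 (2,400 exposed) to 1.22 (1,800) or 1.24 (1,500), still inside Table 5's 1.3. A closed window does not capture later exposure, and later-dispensed pregnancies count as unexposed. The time-updated model keeps them but reports a hazard ratio instead of a prevalence ratio. The propensity-score work must be repeated in four countries.
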